1 SUMMARY

The **medicines' pathway** in nursing homes (NHs) is complex and challenging, resulting in processes that are prone to **medication errors** and **not automatically person-centered**. A need for quality improvement initiatives is present for which a **systems approach**, rather than single initiatives focusing on specific aspects, might be useful.

The Process Optimization Of the Medicines' pAthway in nursing Homes (POOMAH) project will be set up to support Flemish NHs to improve the quality of their medicines' pathway. Objectives of POOMAH include to determine the quality of the medicines' pathway in NHs (i.e. baseline), to explore associations between organizational characteristics of NHs and the quality of the medicines' pathway, and to evaluate and compare the effectiveness of different formats and intensities of support (i.e. access to toolbox, intervision, external coaching or integration of a coordinating pharmacist) provided to NHs to improve the quality of the medicines' pathway.

Outcomes relate to the quality of the medicines' pathway in participating NHs, through the calculation of performance scores. Besides this, a thorough process evaluation will be performed.

In total, support will be provided for approximately 100 NHs in the overall three-year quality improvement project. The allocation of NHs to intervention arms (i.e. different formats and intensities of support) will be executed by means of stratified randomization.

Both quantitative and qualitative data will be collected and will be analyzed by appropriate statistical tests and content/thematic analysis, respectively.

2 SAMENVATTING

Het medicatieproces in woonzorgcentra is complex en uitdagend, wat leidt tot processen die foutgevoelig zijn en niet automatisch persoonsgericht. Er is daardoor nood aan kwaliteitsverbeterende initiatieven met een systeemsgerichte aanpak in plaats van afzonderlijke acties gericht op één specifiek aspect van het medicatieproces.

De POOMAH-studie, ofwel 'Optimalisatie van het medicatieproces in woonzorgcentra' wordt opgericht om Vlaamse woonzorgcentra te ondersteunen in het verbeteren van de kwaliteit van hun medicatieproces.

De doelstellingen van de POOMAH-studie omvatten het in kaart brengen van de huidige kwaliteit van medicatieprocessen in woonzorgcentra, bekijken welke verbanden er mogelijks zijn tussen de kwaliteit van het medicatieproces en organisatorische kenmerken van woonzorgcentra, en om te evalueren welke vorm en mate van ondersteuning het meest effectief is om woonzorgcentra kwaliteitsverbetering te laten realiseren inzake hun medicatieproces.

Uitkomsten die in kaart zullen gebracht worden, hebben betrekking op de kwaliteit van het medicatieproces. Meer bepaald zal er gebruik gemaakt worden van performantiescores. Daarnaast zal ook een grondige procesevaluatie worden uitgevoerd.

In totaal, in de loop van het 3-jaar-durende project, wordt ondersteuning voorzien voor ongeveer 100 woonzorgcentra. De vorm en mate van ondersteuning dat voorzien wordt, wordt bepaald door de interventie-arm waaraan het woonzorgcentrum wordt toegewezen. De toewijzing gebeurt aan de hand gestratifieerde randomisatie.

Zowel kwantitatieve als kwalitatieve data zullen verzameld en geanalyseerd worden, en dit door middel van, respectievelijk, gepaste statistische testen en een content/thematische analyse.

4 INTRODUCTION

The World Health Organization (WHO) defines 'quality of care' as "the degree to which health services for individuals and populations increase the likelihood of desired health outcomes" (1). One of the many health services provided in nursing homes (NHs) is prescribing, administering and monitoring of medication – processes that belong to what is called 'the medicines' pathway'.

Already some years ago, researchers in the UK observed at least one **medication error** in 69.5% of nursing home residents (NHRs) in either the prescribing, dispensing, administration or monitoring process of the medicines' pathway (2). A systematic review by Ferrah et al., on the other hand, indicated that 16 to 27% of NHRs were subject to medication errors in the same processes. Furthermore, they reported that 13-31% of NHRs were exposed to one or more medication errors after a transfer from the hospital to the NH (3). Recent studies in Spain and USA, as well, state that up to 40% of NHRs are exposed to medication errors at NH admission, either when arriving from home or from the hospital (4,5). In Belgium, a recent policy report (October 2022) on the quality of the medicines' pathway in Flemish NHs highlights gaps in the documentation of medication plans, as well as in the processes of medication storage and administration (6).

It is clear that the medicines' pathway in NHs is complex and challenging, resulting in processes that are prone to medication errors and not automatically person-centered. Hence, a need for quality improvement initiatives is present. As errors occur in all steps of the medicines' pathway, and challenges are present not only on resident but also on organizational level, the entirety of the medicines' pathway can be seen as an error-prone system (7). Hence, a **systems approach** to quality improvement, rather than single initiatives focusing on specific aspects, might be useful to reduce the prevalence of medication errors (i.e. to prevent them) and minimize their impact on NHRs (2,3).

As a means to support such systems approach, a framework has been developed by Strauven et al. that describes all medication-related activities in NHs. The framework defines a total of eight processes, going from (re-)admission of the resident over medication prescribing to medication administration and monitoring of medication (side-)effects, supporting the implementation of a safe and effective medicines' pathway. Processes are further divided into key activities (KAs) and best practices (BPs) (8). Following the RESPECT (RESident's Participation in the Evaluation and Customization of Therapy) project, the framework has been updated (2022) to not only support a safe and effective but also a person-centered medicines' pathway in NHs (9–12). The updated version of the framework contains eight processes, 29 KAs and 152 BPs (not yet published, see Appendix 1).

5 OBJECTIVES

The overall aim of the project is to improve the quality of the medicines' pathway in Flemish NHs. As defined by the WHO, quality health services should be **effective**, **safe**, **and person-centered** (13). Hence, quality improvement initiatives should focus on these attributes in order to achieve a qualitative medicines' pathway, one of the many health services provided in NHs. In this regard, the **Process Optimization Of the Medicines' pAthway in nursing Homes** (POOMAH) project will be set up to support Flemish NHs, guided by the aforementioned framework, to improve the quality of their medicines' pathway. Within POOMAH, four specific study objectives can be distinguished:

- 1) To determine the quality of the medicines' pathway in NHs (i.e. baseline)
- 2) To benchmark the quality of the medicines' pathway across NHs (i.e. baseline)
- 3) To explore the association between organizational characteristics of NHs and the quality of the medicines' pathway
- 4) To evaluate and compare the effectiveness of different formats and intensities of support (i.e. access to toolbox, intervision, external coaching or integration of a coordinating pharmacist) provided to NHs to improve the quality of the medicines' pathway (i.e. the primary objective)

6 OUTCOMES

6.1 Primary outcomes

The primary outcome consists of the quality of the medicines' pathway in participating NHs, represented by overall performance scores, measured at the end of the study (i.e. 1 year).

6.2 Secondary outcomes

The number of (psychoactive) medications used by NHRs will be considered as a key secondary outcome. Other secondary outcomes include the quality of processes and important key activities of the medicines' pathway, represented by process-specific and activity-specific performance scores, respectively, and the number of falls and hospitalizations of NHR.

6.3 Process evaluation

As proposed by the Medical Research Council (MRC), implementation of the intervention will be monitored through a process evaluation in order to clarify causal mechanisms and to identify contextual factors that might explain variation in outcomes (14).

Experiences of NH staff, NHRs and relatives (as considered relevant in each NH) with regard to their participation in the quality improvement project will be explored thoroughly, as well as the perspectives of external coaches and coordinating pharmacists on supporting NHs in their quality

improvement initiatives. Furthermore, a thick description will be made of quality improvement initiatives set up in NHs.

7 METHODOLOGY

7.1 Study design

The POOMAH study consists of a multi-arm pre-post cluster randomized controlled trial (RCT) in Flemish NHs. Nursing homes will perform a quality assessment of their medicines' pathway at baseline and will accordingly set up and monitor quality improvement initiatives. Hence, quality improvement initiatives can be expected to differ across participating NHs. A thorough process evaluation will be performed simultaneously.

Before progressing to the cluster RCT, a pilot study will be performed to assess the feasibility of executing the large-scale cluster RCT (e.g. participant recruitment, data collection, etc.).

7.2 Intervention arms

During the quality improvement project, support will be provided to NHs as a means to improve the quality of their medicines' pathway. Four different intervention arms (i.e. Tracks), providing different formats and intensities of support to NHs during one year, can be distinguished (see Figure 1).

[figure not shown]

Figure 1: Four tracks of support in the quality improvement project

Nursing home staff will be made aware that the support provided in the context of the POOMAH study is of a temporary nature. Hence, the provided support (i.e. access to toolbox, intervision, external coaching, integration of a coordinating pharmacist) ends at conclusion of the study. Should NHs be willing to extend their access to the toolbox, the external coaching or the integration of a coordinating

pharmacist after conclusion of the study, NHs are expected to set up adequate agreements with KU Leuven (for the toolbox), or with external coaches or coordinating pharmacists on an individual basis, using their own financial resources if applicable.

7.2.1 Access to toolbox

All NHs will gain access to a (mainly digital) toolbox. This toolbox provides educational material and instruments that have been developed as part of earlier research projects (i.e. the Come-On study and the RESPECT-project). Tools include an e-learning on appropriate prescribing for NHRs, knowledge clips on goal-oriented care and medication decision-making, the RESPECT-tool to explore residents' personal health and life goals, the RESPECT-brochure to inform NHRs with regard to the medicines' pathway, etc. An overview of all educational materials and instruments that will be made available at the start of the project can be found in Appendix 2.

In addition to the digital part of the toolbox, a book will be made available for NHs. Each NH will receive four copies of the book. This book, authored by the research team, will offer detailed information about the medicines' pathway and how to improve the quality of the medicines' related processes.

Nursing homes will have access to the toolbox during their participation in the quality improvement project. If NHs want to keep using the toolbox after conclusion of the project, an appropriate agreement will be made up between the NH and the KU Leuven.

7.2.2 Intervision

Nursing homes assigned to Track 2, 3 and 4 will be invited to take part in intervision with fellow NHs. During these meetings, NHs will share experiences with regard to the evaluation and optimization of their medicines' pathway. Six intervision meetings will be organized during the POOMAH-study, for each intervention arm. Within each intervention arm, NHs will be grouped into smaller clusters of three to six NHs based on region. The intervision meetings will be organized in these smaller clusters in specific weeks, that will be communicated on beforehand (current planning: week 10/02; week 17/03; week 05/05; week 16/06; week 29/09; week 17/11).

Meetings will be conducted in real life at the participating NHs. Each NH will host at least one intervision meeting, with the hosting NHs responsible for organizing and moderating the meeting. The research team (VF, AD, AF) will provide all material needed for each intervision meeting, including a topic guide and supporting slides. .

To prepare the hosting NHs for their role, the research team will organize an online 'train the trainer' session one week before each intervision meeting. Per intervention arm, the project coordinators of the NHs that will host that specific intervision meeting, will be invited to the 'train the trainer' session.

During these sessions the NHs will receive comprehensive information on managing the intervision meeting and will go through the supportive material in detail.

Additionally, bi-monthly intervision meetings will be organized with external coaches (track 3) and with coordinating pharmacists (track 4). These intervision meetings will mainly be performed online, and will be moderated by the research team (AF, AD, VF).

7.2.3 External coaching

Nursing homes in Track 3 will receive six to eight visits (for a total of 12 guidance hours) from an external coach, e.g. someone who independently guides NH teams in their quality improvement efforts. External coaches are no members of the interprofessional team present in each NH, i.e. they remain independent. The NH itself is responsible for setting up and implementing initiatives to improve the quality of their medicines' pathway. During each visit, external coaches consult with the local project team and listen to their experiences with regard to setting up and implementing quality improvement initiatives. Accordingly, they can provide tips and tricks in order to help them with the development or implementation of their actions.

Between visits, NHs are allowed to consult the external coach for short questions, etc. However, the number of such 'extra' consultations should be limited to a minimum.

External coaches will have completed the lifelong learning course 'Coordinating pharmacist in nursing homes' (15), and will on their turn be supervised by the research team. Some of these pharmacists are already involved in supplying medication to NHs. If so, these pharmacists will be assigned to a NH they currently supply, provided it is geographically feasible. If no NH they supply is selected for the study in track 3, or if no match can be made, these pharmacists can be assigned a role as external coach to a NH that they do not deliver, based on geographical accessibility.

Pharmacists who are not involved in supplying NHs, will be assigned to NHs based on geographical accessibility. This approach ensures that both pharmacists who currently supply NHs and those who do not, are recruited, allowing for an exploration of both perspectives during the quality assessment of this study.

An agreement between KU Leuven and each external coach will be made up for the duration of the POOMAH study. This agreement includes a deontological clause which states that in carrying out the project, the deontological rules must be respected, and activities (actions) intended to promote or that could be interpreted as an attempt to promote their own pharmacy (or pharmacy group) must be avoided.

Furthermore, external coaches will be financially compensated for their contributions. Should NHs be willing to extend the services provided by the external coach beyond the support foreseen in the project, NHs are expected to set up an adequate agreement with the external coach themselves.

7.2.4 Integration of a coordinating pharmacist

A coordinating pharmacist will be integrated in the care team of each NH assigned to Track 4. The pharmacist will be present for 78 hours, spread over the whole intervention year. Coordinating pharmacists will become members of the interprofessional team present in each NH, i.e. they do not remain independent. The coordinating pharmacist leads the development and implementation of initiatives to improve the quality of the NH's medicines' pathway. He/she can therefor perform observations of the medicines-related processes in the NH, have in-dept discussions with HCPs active in the NH (including general practitioners),... Additionally, the coordinating pharmacist, as an active member of the care team, can talk with residents about medication, perform medication reviews, give training to nurses and care aids, participate in interprofessional discussions on a NHRs care plan,... Coordinating pharmacists will have completed the lifelong learning course 'Coordinating pharmacist in nursing homes' (15), and will on their turn be supervised by the research team. Some of these pharmacists are already involved in supplying medication to NHs. If so, these pharmacists will be assigned to a NH they currently supply, provided it is geographically feasible. If no NH they supply is selected for the study in track 4, or if no match can be made, these pharmacists can be assigned a role as coordinating pharmacist to a NH that they do not deliver, based on geographical accessibility. Pharmacists who are not involved in supplying NHs, will be assigned to NHs based on geographical accessibility. This approach ensures that both pharmacists who currently supply NHs and those who do not, are recruited, allowing for an exploration of both perspectives during the quality assessment of this study.

An agreement between KU Leuven and each coordinating pharmacist will be made up for the duration of the POOMAH study. This agreement includes a deontological clause which states that in carrying out the project, the deontological rules must be respected, and activities (actions) intended to promote or that could be interpreted as an attempt to promote their own pharmacy (or pharmacy group) must be avoided.

Furthermore, coordinating pharmacists will be financially compensated for their contributions. Should NHs be willing to extend the services provided by the coordinating pharmacist beyond the support foreseen in the project, NHs are expected to set up an adequate agreement with the coordinating pharmacist themselves.

7.3 Data collection

7.3.1 Quantitative data

Quality assessment

In each NH, a quality assessment of the medicines' pathway will occur at baseline (i.e. before) and at the end of the study (i.e. after). This assessment will be performed through the quick scan of the two-part quality assessment instrument that has been recently developed by our research group (see Appendix 3) (16). The quick scan is based on the KAs as defined in the framework of the medicines' pathway. For this quick scan, these KAs have been adjusted for readability during the pilot study. This way, the KAs are more understandable for each member of the interdisciplinary team in the NHs. The quick scan applies the importance-performance analysis (IPA) methodology, a method that has been successfully used in healthcare to identify quality aspects with the highest priority. In such assessment, respondents are asked to score both the importance and current performance of items under assessment (i.e. KAs) (17,18). The results of this analysis can be visualized on an IPA-graph that plots performance on the x-axis and importance on the y-axis. Four quadrants are formed in this process: "Concentrate Here" (high importance, low performance), "Keep up the Good Work" (high importance, high performance), "Low Priority" (low importance, low performance), and "Possible Overkill" (low importance, high performance) (19).

The only criterion applied with regard to respondents in the quick scan, is that they need to be involved in the medicines' pathway of the NH (e.g. coordinating physician, nurses, nurse aids, pharmacist, ...). Respondents are asked to score the performance of each KA (i.e. To what degree is the KA performed as described?) using a 5-point Likert scale with response options 'Absolutely so', 'Rather so', 'A little', 'Rather not', 'Absolutely not'. Likewise, respondents are invited to score the importance of each KA (i.e. How important is it that the KA is performed as described?) by means of a 4-point Likert scale, including response options 'Very important', 'Rather important', 'Rather not important', and 'Not important'.

The quick scan is available in Limesurvey®, an online survey platform, and will be sent to the project coordinators of participating NHs. Project coordinators will be invited to complete the questionnaires themselves and to further distribute the quick scan to NH staff they consider relevant.

Next, the quality of the three processes 'storage', 'preparation' and 'administration' will be investigated using the detailed scan. This scan consists of 68 questions, to be answered on a five-point Likert Scale (see Appendix 17). This scan is also available in Limesurvey®. Only nurses and headnurses will be asked to complete this survey.

Other parts of the detailed scan can voluntarily be used by NHs to gain further insight in the quality of their medication process. The answers on these 'other parts' of the detailed scan are only for the NHs

to get more insight in these key activities, but will not be further used for data collection by the research team. In this way, these other parts of the detailed scan can be interpreted as just another tool of the toolbox.

Organizational characteristics

A survey has been developed, based on (inter)national literature and experiences from previous research projects, to map several organizational characteristics (see Appendix 4). The survey is divided into five categories, based on the System Engineering Initiative for Patient Safety (SEIPS) model: 1) persons, 2) tasks, 3) environment, 4) organization, and 5) technology and tools (20). The survey collects data on the number of residents and nurses employed at the NH (i.e. persons), on pharmacy services (i.e. tasks), on type pharmacy that delivers medication to the NH (i.e. environment), on the organization of medical pharmaceutical concertation (i.e. organization), on the types of patient files used (i.e. technology and tools), etc.

The survey on organizational characteristics will be made available in Limesurvey[®]. It will be sent to the project coordinator of each NH who will be asked to complete it.

Number of (psychoactive) drugs used by NHRs

The Flemish center of expertise in alcohol and other drugs (Vlaams expertisecentrum Alcohol en andere Drugs, VAD) provides a manual for NHs to develop a policy on the use of psychoactive medications by NHRs(21). The manual includes a monitoring tool for NHs to map the (psychotropic) medication use by NHRs, clinical outcomes (falls, hospitalizations), and the number of local interdisciplinary meetings. All data are collected on an institutional level; no data on individual residents are registered.

In POOMAH, this monitoring tool will be used to collect data on the number of (psychoactive) drugs used by NHRs, and the number of falls and hospitalizations. By comparing the number of (psychoactive) drugs used, falls and hospitalizations at the beginning and at the end of the intervention year, the impact of the project on prescribing (e.g. changes in number of chronic (psychoactive) medications used by NHRs) can be investigated.

The local project coordinator will be asked to complete the monitoring tool (Appendix 18) in collaboration with the supplying pharmacist, according to the instructions provided in the VAD manual, in the beginning (i.e. February) and at the end (i.e. December) of the intervention year.

Demographic data

Demographic data will be collected of each NH (see 'Organizational characteristics'). Moreover, healthcare professionals participating in the NH's project team will be asked to complete a survey to collect their demographics (see Appendix 5). The same survey will be used to map demographic data

of healthcare professionals participating in interviews or focus groups (see '6.3.2 Qualitative data'). A tailored survey will collect demographics of nursing home residents and relatives participating in interviews or focus groups (see Appendix 6 and 7).

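### The quick-scan respondent rule lets study-paid pharmacists in Tracks 3 and 4 rate their own work on the primary outcome, and the respondent-type adjustment removes the resulting bias only in part of the cases

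*Protocol*

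**What the plan says.** **Who scores the primary outcome.** Section 7.3.1 of the protocol states: "The only criterion applied with regard to respondents in the quick scan, is that they need to be involved" in the nursing home's medicines' pathway. The examples given are "e.g. coordinating physician, nurses, nurse aids, pharmacist". The local project coordinator answers and is asked "to further distribute the quick scan to NH staff they consider relevant". By contrast, the same section limits the detailed scan to nurses and head nurses.

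**Who delivers Track 4.** Section 7.2.4: "Coordinating pharmacists will become members of the interprofessional team present in each NH, i.e. they do not remain independent". It adds: "The coordinating pharmacist leads the development and implementation of initiatives". The role is paid.

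**Who delivers Track 3.** Section 7.2.3 describes external coaches as independent and outside the care team, also paid. For pharmacists who already supply nursing homes, however, "these pharmacists will be assigned to a NH they currently supply, provided it is geographically feasible". Section 7.2.4 has the same rule for Track 4.

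**How the outcome is analysed.** Section 7.4.1 scores each respondent by the proportion of key activities rated as implemented. It fits a linear mixed model with random effects of home and respondent. Track-by-time is the effect of interest, and respondent type enters as a main effect only. The section expects most respondents to answer at both times.

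**Key secondary outcome.** The project coordinator completes the monitoring tool "in collaboration with the supplying pharmacist".

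**The concern.** No section excludes a coach or coordinating pharmacist from the quick scan. A coordinating pharmacist meets the only criterion by becoming a team member. A coach meets it where he or she also supplies the home. Either may then judge, at the end of the study, how well the pathway performs after a year of their own paid support.

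Tracks 1 and 2 have no such person. Any tendency of deliverers to rate differently from other staff therefore enters the comparison of tracks, which is the primary objective (section 5, objective 4). Section 8 uses the initial performance score to stratify the randomisation, so baseline scores precede allocation. A supplying pharmacist can thus answer at baseline with no study role and at follow-up as the paid deliverer in the same home.

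**Working it through.** The protocol gives no power, standard deviation or effect figure (section 8 says that no sample size calculation was made), so there is nothing to reproduce. The check asks what the planned model does with such a respondent.

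**Inputs from the protocol:** 29 key activities (7.4.2); the model terms (7.4.1); about 100 homes in four tracks, so 100/4 = 25 per track if split equally.

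**Assumptions, not in the documents:**
- *m* = 8 quick-scan respondents per home, range 5 to 15. Section 8 aims for at least 3 team members and 5 other staff, but does not call them quick-scan respondents.
- One of the *m* is the study pharmacist, whose follow-up score rises by *b* = 10, 20 or 30 points more than colleagues' scores. This is about 3, 6 or 9 of 29 activities (3/29 = 10.3%).
- No true difference between tracks.

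**Step 1. The same pharmacist answers before and after.** The respondent-type effect is equal at both times and cancels from the change. The spurious track-by-time effect is *b/m*:
- *m* = 8: 10/8 = 1.25, 20/8 = 2.5, 30/8 = 3.75 points.
- With shifts of exactly 3, 6 and 9 activities: 2.1, 4.1, 6.2 points at *m* = 5; 1.3, 2.6, 3.9 at *m* = 8; 0.7, 1.4, 2.1 at *m* = 15.

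Solving the planned model's generalised least-squares equations (assumed SDs of 6 for home, 8 for respondent and 8 for residual) returns the same values. The type effect removes none of the bias.

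**Step 2. The pharmacist answers only at follow-up.** The same equations give:
- pharmacists in the other track answer at both times: 0.4, 0.7, 1.1 points at *m* = 8;
- no other pharmacist answers anywhere: 0, because the type effect absorbs the whole shift.

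**Step 3. Only some homes are affected.** With a share *s* of the track's homes in the Step 1 situation, the shift is *s* × *b/m*. For *s* = 0.5 and *m* = 8 it is 0.63, 1.25, 1.88 points; for *s* = 0.25 it is 0.31, 0.63, 0.94.

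**Step 4. What this could do to a test.** Assume a respondent SD of 20 points (variance 400), a residual variance share of 0.42 and a home-by-time share of 0.03.
- Variance of a home's mean change = 2 × 0.42 × 400/8 + 2 × 0.03 × 400 = 42 + 24 = 66.
- SE of the difference between two tracks = √(2 × 66/25) = 2.30 points.
- False-positive rate = P(|Z + shift/SE| > 1.96), against a nominal 5%:

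| Situation | *b* = 10 | *b* = 20 | *b* = 30 |
|---|---|---|---|
| All homes affected, before and after | 8.5% | 19% | 37% |
| Half affected | 5.9% | 8.5% | 12.9% |
| A quarter affected | 5.2% | 5.9% | 6.9% |

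The first row is the extreme, not the expected case.

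**The case against.** The strongest reply is that the protocol permits this but does not require it. Distribution is to staff whom the coordinator thinks relevant. Only some of the pharmacists supply nursing homes, matching depends on track and geography, and non-suppliers are recruited on purpose. A newly integrated coordinating pharmacist has no baseline record and falls under Step 2, where the planned model handles the problem largely or fully. Direction is also open: a trained pharmacist who has observed the processes could score them lower than before. All of this stands, and it limits the size.

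A reader might infer more in three places.

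- **That a bias is built into the track comparison and the model cannot remove it.** This holds only for a pharmacist who answers at both times. The false-positive rates of 8.5%, 19% and 37% also need every home in the track to be in that situation, which sections 7.2.3 and 7.2.4 make unlikely.
- **That Tracks 1 and 2 are free of self-rating.** They are not. In all tracks the local team sets up the initiatives and the coordinator both answers and chooses respondents. Only the study-paid deliverer is specific to Tracks 3 and 4.
- **That the key secondary outcome is equally exposed.** The supplying pharmacist helps with the monitoring tool in all tracks and at both times. The data are institution-level counts, and a non-supplying coordinating pharmacist has no stated role. The overlap is minor and arises only where the study pharmacist also supplies the home.

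The reply does not reach the respondent rule itself, which section 7.3.1 fixes and which contains no exclusion. Sections 7.2.3 and 7.2.4 even say that the mix of pharmacists allows both perspectives to be explored during the quality assessment. That may be a slip for the qualitative part, but as written it does not suggest that these pharmacists stay out of the scoring.

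**Conclusion.** The point holds as a gap in the respondent rule. As written, deliverers in two of the four tracks may rate their own work on the primary outcome, and the main effect for respondent type does not protect the track-by-time contrast when a supplying pharmacist answers before and after. The size is uncertain: 1.25 to 3.75 points with one of eight respondents inflating by 10 to 30 points in every home, half of that if half the homes are affected, and 0 to 1.1 points if the pharmacist answers only at follow-up. All these figures rest on assumed inputs, and the documents do not establish the direction. The gap is worth closing because closing it is cheap, not because a material bias has been shown.

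**What to change.** 1. Add to section 7.3.1 that external coaches and coordinating pharmacists contracted for the study do not complete the quick scan for the nursing home they support.
2. Flag any baseline record from a person who later takes such a role. The respondent category for pharmacists does not separate study-paid from other pharmacists, so the flag has to be recorded.
3. Base the primary analysis on non-pharmacist respondents in all tracks at both time points, with an all-respondent analysis as sensitivity. Removing pharmacists only from Tracks 3 and 4 would make the respondent mix differ between tracks after randomisation.

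With these changes this source of bias is zero by construction. Self-rating by staff, common to all tracks, remains.

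**Cost.** About one respondent per home, and the pharmacist's view no longer counts in the primary score. Under the Step 4 assumptions, going from 8 to 7 respondents changes the variance from 66 to 336/7 + 24 = 72, and the SE from 2.30 to √(2 × 72/25) = 2.40 points, about 4% wider.

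The monitoring tool needs no new data source. An extract from the supplying pharmacy would come from the same party and would not be more independent.
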